5. INVESTIGATIONAL MEDICINAL PRODUCTS

5.1. Randomization and Blinding

Not applicable.

5.2. Ledipasvir/Sofosbuvir Fixed-Dose Combination

5.2.1. Description and Handling

5.2.1.1. Formulations

5.2.1.1.1. LDV/SOF FDC 90 mg/ 400 mg tablets

LDV/SOF FDC 90 mg/400 mg tablets are orange, diamond-shaped, film-coated tablets containing 90 mg of LDV and 400 mg of SOF. The tablets are debossed with “GSI” on one side and “7985” on the other side. The LDV/SOF FDC tablets contain the following inactive ingredients: lactose monohydrate, copovidone, microcrystalline cellulose, croscarmellose sodium, colloidal silicon dioxide, magnesium stearate, polyvinyl alcohol, titanium dioxide, talc, polyethylene glycol, FD&C yellow # 6 /sunset yellow FCF aluminum lake.

Placebo to match LDV/SOF FDC 90 mg/ 400 mg tablets for the Swallowability Assessment are orange, diamond-shaped, film-coated tablets debossed with “GSI” on one side and “7985” on the other side. The tablets contain lactose monohydrate, copovidone, microcrystalline cellulose, croscarmellose sodium, magnesium stearate, polyvinyl alcohol, titanium dioxide, talc, polyethylene glycol, FD&C yellow # 6 /sunset yellow FCF aluminum lake.

5.2.1.1.2. LDV/SOF FDC 22.5 mg/ 100 mg tablets

Age-appropriate formulations of LDV/SOF FDC have been developed for subjects who are unable to swallow the LDV/SOF FDC 90 mg/ 400 mg tablets which include a lower dose strength tablet (LDV/SOF FDC 22.5 mg/100 mg) formulation. LDV/SOF FDC lower dose strength tablets are round, plain-faced, white film-coated tablets containing 22.5 mg of LDV and 100 mg of SOF. The LDV/SOF FDC lower dose strength tablets contain the following inactive ingredients: lactose monohydrate, copovidone, microcrystalline cellulose, croscarmellose sodium, colloidal silicon dioxide, magnesium stearate, polyvinyl alcohol, titanium dioxide, talc, and polyethylene glycol.

Placebo to match LDV/SOF FDC 22.5 mg/ 100 mg tablets for the Swallowability Assessment are round, plain-faced, white film-coated tablets. The placebo tablets contain the following inactive ingredients: lactose monohydrate, copovidone, microcrystalline cellulose, croscarmellose sodium, magnesium stearate, polyvinyl alcohol, titanium dioxide, talc and polyethylene glycol.

5.2.1.1.3. LDV/SOF FDC Oral Granules

The LDV/SOF FDC oral granules 11.25 mg/ 50 mg are orange, round, film-coated granules. The LDV/SOF FDC oral granules contain the following inactive ingredients: lactose monohydrate, copovidone, microcrystalline cellulose, croscarmellose sodium, colloidal silicon dioxide, magnesium stearate, hypromellose, talc, polyethylene glycol, titanium dioxide, iron oxide yellow, iron oxide red, and amino methacrylate copolymer.

5.2.1.2. Packaging and Labeling

5.2.1.2.1. LDV/SOF FDC 90 mg/ 400 mg tablets

LDV/ SOF FDC 90 mg/ 400 mg tablets are packaged in white, high density polyethylene (HDPE) bottles. Each bottle contains 28 or 30 tablets, a silica gel desiccant, and polyester packing material. Each bottle is enclosed with a white, continuous thread, child resistant screw cap with an induction-sealed, aluminum faced liner.

Placebo tablets to match LDV/SOF FDC 90 mg/ 400 mg tablets for the Swallowability Assessment are packaged in white, high density polyethylene (HDPE) bottles. Each bottle contains 30 tablets, a silica gel desiccant and polyester packing material. Each bottle is enclosed with a white, continuous thread, child resistant screw cap with an induction-sealed, aluminum faced liner.

5.2.1.2.2. LDV/SOF FDC 22.5 mg/ 100 mg tablets

LDV/SOF FDC 22.5 mg/ 100 mg tablets are packaged in white, high density polyethylene (HDPE) bottles. Each bottle contains 30 tablets, a silica gel desiccant, and polyester packing material. Each bottle is enclosed with a white, continuous thread, child resistant screw cap with an induction-sealed, aluminum faced liner.

Placebo tablets to match LDV/SOF FDC 22.5 mg/ 100 mg tablets for Swallowability Assessment are packaged in white, high density polyethylene (HDPE) bottles. Each bottle contains 30 tablets, a silica gel desiccant and polyester packing material. Each bottle is enclosed with a white, continuous thread, child resistant screw cap with an induction-sealed, aluminum faced liner.

5.2.1.2.3. LDV/SOF FDC oral granules

The LDV/SOF FDC 11.25 mg/ 50 mg oral granules are packaged in aluminum foil packets. A prespecified number of packets will be packaged into cartons for dispensation to subjects at clinical sites.

All LDV/SOF FDC tablets, oral granules, and placebo to match LDV/SOF FDC bottles to be distributed in the US, EU, and the rest of the countries shall be labeled to meet all applicable requirements of the US Food and Drug Administration (FDA), Annex 13 of Good Manufacturing Practices: Manufacture of investigational medicinal products (February 2010), and/or other local regulations as applicable.

5.2.2. Storage and Handling

LDV/ SOF FDC 90 mg/ 400 mg tablets, 22.5 mg/ 100 mg tablets, and 11.25 mg/ 50 mg packets should be stored at controlled room temperature until required for administration. Controlled room temperature is defined as 25 °C (77 °F); excursions are permitted between 15 °C and 30 °C (59 °F to 86 °F).

Placebo to match LDV/SOF FDC tablets, 90 mg/ 400 mg, and 22.5 mg/ 100 mg, for the Swallowability Assessment should be stored at controlled room temperature until required for administration. Controlled room temperature is defined as 25 °C (77 °F); excursions are permitted between 15 °C and 30 °C (59 °F to 86 °F).

All drug products should be stored in a securely locked area, accessible only to authorized site personnel. To ensure the stability of the Investigational Medicinal Product (IMP) and to ensure proper product identification, the drug product should not be stored in a container other than the container in which they are supplied. Consideration should be given to handling, preparation, and disposal through measures that minimize drug contact with the body. Appropriate precautions should be followed to avoid direct eye contact or exposure through inhalation when handling LDV/SOF FDC.

Sufficient quantities of LDV/SOF FDC tablets, oral granule packets, and placebo tablets will be shipped to the investigator or qualified designee from Gilead Sciences (or its designee).

5.2.3. Dosage and Administration of LDV/SOF FDC

PK Lead-in Phase:

Cohort 1: LDV/SOF FDC 90 mg/ 400 mg tablets will be administered once daily with or without food. Subjects determined unable to swallow the placebo to match the 90 mg/ 400 mg LDV/SOF FDC tablet (via LDV/SOF FDC Placebo Swallowability Assessment at Screening up to Day 1) will be re-assigned to 4 × 22.5 mg/ 100 mg tablets daily. Subjects who weigh < 45 kg will be excluded.

Cohort 2: LDV/SOF FDC 2 × 22.5 mg/ 100 mg tablets will be administered once daily with or without food. Subjects must weigh ≥ 17 kg and < 45 kg.

Cohort 3: LDV/SOF FDC oral granules 45 mg/ 200 mg (4 × 11.25 mg/ 50 mg packets) will be administered once daily with or without food for subjects weighing ≥ 17 kg. LDV/SOF FDC oral granules 33.75 mg/ 150 mg (3 × 11.25 mg/ 50 mg packets) will be administered once daily with or without food for subjects weighing < 17 kg.

Intensive PK and safety results from the PK Lead-in Phase of each cohort will be reviewed to confirm the appropriateness of the evaluated LDV/SOF FDC dose for the Treatment Phase of that cohort as well as to determine the age-appropriate dose to be evaluated in the PK Lead-in phase of the next cohort.

Treatment Phase: Subjects who participated in the PK Lead-in Phase of each cohort will continue in the Treatment Phase with no interruption of study drug administration until the appropriateness of the dose is confirmed by PK and safety data from the PK-Lead-in Phase. Additional subjects will be enrolled in the Treatment Phase of each cohort upon confirmation of the appropriateness of the dose.

Subjects should be instructed that if vomiting occurs within 5 hours of dosing an additional tablet should be taken. If vomiting occurs more than 5 hours after dosing, no further dose is needed.

If a dose is missed and it is within 18 hours of the normal time, subjects should be instructed to take the tablet as soon as possible and then subjects should take the next dose at the usual time. If it is after 18 hours then subjects should be instructed to wait and take the next dose at the usual time. Subjects should be instructed not to take a double dose.

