6.3.1.1. Drug Administration

- Dispense study drug(s) as directed by the IWRS
- Instruct the subject on the packaging, storage and administration of study drug
- Perform LDV/SOF FDC swallowability assessment (for subjects administered LDV/SOF FDC in tablet form only if not previously completed at screening). Observe the subject taking the first dose of study drug (with or without food) and record the time of first dose
- Subjects will be administered a dosing diary with instructions.

6.3.2. Day 3

The following procedures/assessments are to be completed on Day 3:

- Perform a symptom-directed physical examination as needed
- Vital signs, including body weight and height
- Assessment of AEs and concomitant medications
- Review medication compliance with subject and/or subject's parent/guardian
- Obtain blood samples for:
 - Hematology
 - Chemistry
 - HCV RNA
 - Viral sequencing (archive)
- Review subject dosing diary

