6.4.1.1. Drug Administration

- Dispense study drug as directed by the IWRS
- GT-3 subjects only: Instruct the subject on the appropriate RBV dose after weight-based dosage is calculated using Day 1 weight
- Instruct the subject on the packaging, storage, and administration of study drug
- Observe the subject taking the first dose of study drug (with or without food) and record the time of first dose

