1.2.2. Treatment Phase

Additional HCV-infected children will be enrolled into the Treatment Phase upon confirmation of the appropriateness of the dose from the PK Lead-in Phase. The Treatment Phase will be initiated sequentially by age group as defined in Cohorts 1, 2, and 3 of the PK Lead-in Phase.

Subjects who participated in the PK Lead-in Phase will immediately roll over into the Treatment Phase with no interruption of study drug administration until the appropriateness of the dose has been confirmed by PK and safety results from the PK Lead-in Phase. The first visit in the Treatment Phase for these subjects will be the Week 2 visit.

After dose confirmation in the PK Lead-in Phase of each age group, the identical dose was used in subjects of the corresponding age group enrolled in the Treatment Phase.

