4.2.2. Adherence to Study Drug

The level of adherence to individual study drug will be assessed separately based on the total amount of individual study drug administered relative to the total amount of individual study drug prescribed. In this study, LDV/SOF FDC 90/400 mg tablets, LDV/SOF FDC 22.5/100 mg tablets, and LDV/SOF 11.25/50 mg packets containing granules have been used. For RBV, both REBETOL capsules and REBETOL RBV oral solution could be used. Each capsule contains 200 mg RBV and the oral solution contains 40 mg RBV per mL.

Given the fact that multiple formulations of the study drug have been used in this study, the adherence will be calculated based on the amount of LDV/SOF FDC (mg) or RBV (mg) by the following formula:

$$\text{Level of Adherence(\%)} = \left(\frac{\text{Total Amount of Study Drug Administered}}{\text{Total Amount of Study Drug Prescribed at baseline}} \right) \times 100$$

Where the presumed total amount of study drug (mg) administered to a subject will be determined by the data collected on the drug accountability eCRF using the following formula:

$$\text{Total Amount of Study Drug (mg) Administered} = (\sum \text{Total Amount of Study Drug (mg) Dispensed}) - (\sum \text{Total Amount of Study Drug (mg) Returned})$$

Note: If calculated adherence is greater than 100%, the result will be set to 100%.

The total amount of prescribed LDV/SOF FDC (mg) for 12 weeks and 24 weeks are as follows:

Age Group and Body Weight	LDV/SOF Daily Dose	Total Amount of LDV/SOF Prescribed for 12 Weeks	Total Amount of LDV/SOF Prescribed for 24 Weeks
12 to <18 years any weight	490 mg/day	41160 mg	N/A*
6 to <12 years any weight	245 mg/day	20580 mg	41160 mg
3 to <6 years weighing ≥17 kg	245 mg/day	20580 mg	N/A*
3 to <6 years weighing <17 kg	183.75 mg/day	15435 mg	N/A*

*Note: No subject 12 to <18 or 3 to <6 years old was assigned to 24 weeks of treatment.

For subjects infected with HCV GT3, RBV was prescribed by weight at baseline. The total amount of RBV (mg) prescribed for 24 weeks is as follows:

Body Weight kg (lbs.)	RBV Daily Dose	RBV Number of Capsules	Total Amount of RBV Prescribed for 24 Weeks
<47 (<103)	15 mg/kg/day	Use Oral Solution. Divided dose in the morning and evening.	2,520 mg/kg
47-49 (103-108)	600 mg/day	1 × 200-mg capsules A.M. 2 × 200-mg capsules P.M.	504 capsules (100800 mg)
50-65 (110 – 143)	800 mg/day	2 × 200-mg capsules A.M. 2 × 200-mg capsules P.M.	672 capsules (134400 mg)

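### The vomiting rule in Protocol 5.2.3 calls for one extra tablet, which is a full repeat dose for only one of the five dose presentations and for no planned Group 2 dose

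*Protocol*

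**What the plan says.** Protocol 5.2.3 first gives the dose for each PK Lead-in cohort. Cohort 1 takes the 90/400 mg tablet, or four 22.5/100 mg tablets if the larger tablet cannot be swallowed. For Cohort 2, "LDV/SOF FDC 2 × 22.5 mg/ 100 mg tablets will be administered once daily with or without food". Cohort 3 takes granules, in four packets at 17 kg or above and three packets below 17 kg.

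A paragraph on the Treatment Phase follows, and then a rule with no limit by cohort, age, strength or formulation: "if vomiting occurs within 5 hours of dosing an additional tablet should be taken". Its companion sentence reads: "If vomiting occurs more than 5 hours after dosing, no further dose is needed".

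SAP 1.2.2 carries the lead-in doses forward. After confirmation, "the identical dose was used in subjects of the corresponding age group enrolled in the Treatment Phase". The prescribed-amount table in SAP 4.2.2 has a row for "6 to <12 years any weight" at 245 mg/day.

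On how the rule reaches families, Protocol 6.3.1.1 (PK Lead-in) says "Subjects will be administered a dosing diary with instructions", and Protocol 6.4.1.1 (Treatment Phase) says "Instruct the subject on the packaging, storage, and administration of study drug". Neither restates the vomiting rule by formulation.

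**The concern.** The rule uses a unit that is right for the adult tablet only. Section 5.2.3 counts tablets when it defines doses, so an additional tablet naturally reads as one tablet. A child on two or four small tablets who follows it repeats part of the dose, and a child on granules has no tablet to repeat.

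This is an operative dosing instruction in a paediatric trial, in which one whole age group takes multi-unit doses. A site that teaches it exactly as written under-replaces the dose after early vomiting. A site that sensibly repeats the full dose departs from the protocol text. Sites could therefore handle the same event differently.

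**Working it through.** **Inputs.** Units per dose and strength per unit come from Protocol 5.2.3. The daily amounts used as a check come from SAP 4.2.2. Planned group sizes come from Protocol 3.1.2.

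**Reproducing the stated doses** (units × strength per unit; LDV plus SOF compared with the SAP daily amount):

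| Presentation | LDV/SOF per dose | Sum | SAP daily amount |
|---|---|---|---|
| 1 × 90/400 mg tablet | 90/400 mg | 490 mg | 490 mg |
| 4 × 22.5/100 mg tablets | 90/400 mg | 490 mg | 490 mg |
| 2 × 22.5/100 mg tablets | 45/200 mg | 245 mg | 245 mg |
| 4 × 11.25/50 mg packets | 45/200 mg | 245 mg | 245 mg |
| 3 × 11.25/50 mg packets | 33.75/150 mg | 183.75 mg | 183.75 mg |

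All five agree.

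**Share replaced by one tablet** = 1 ÷ tablets per dose:

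- Single 90/400 mg tablet: 1/1 = 100%.
- Two 22.5/100 mg tablets: 22.5/45 = 100/200 = 50%. Not replaced: 45 − 22.5 = 22.5 mg LDV and 200 − 100 = 100 mg SOF.
- Four 22.5/100 mg tablets: 22.5/90 = 100/400 = 25%. Not replaced: 90 − 22.5 = 67.5 mg LDV and 400 − 100 = 300 mg SOF.
- Four or three granule packets: undefined, because there is no tablet.

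The rule therefore gives a full repeat dose for 1 of 5 presentations.

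**If a site read 'tablet' as 'packet'** (an assumption; the rule does not say so): 11.25/33.75 = 33% of the three-packet dose, leaving 22.5/100 mg; 11.25/45 = 25% of the four-packet dose, leaving 33.75/150 mg.

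**Group 2 (3 to <12 years).** The planned doses are two small tablets, four packets or three packets. The SAP's 245 mg/day for ages 6 to <12 holds at any weight, so heavier children in that age band do not move to the single adult tablet. The rule fits 0 of these 3 presentations. Group 2 is about 120 of 220 planned subjects. Protocol 6.6.7 also sends any subject who cannot swallow the 22.5/100 mg tablet to granules, which adds cases with no tablet to repeat.

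**Does other text repair the rule?** No.

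- Sections 6.3.1.1 and 6.4.1.1 only require that subjects be instructed or given a diary.
- Section 5.4 covers forgotten doses in GT-3 subjects, not vomiting.
- The missed-dose sentence in 5.2.3 also refers to the tablet, but it speaks of a dose that was missed and of the next dose, so the full dose is implied. No under-replacement is claimed there.

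**The case against.** The best reply is that the intent is plain. The rule speaks of dosing and the companion sentence of a further dose, so staff would read 'tablet' as adult-formulation shorthand for the assigned dose, just as they would in the missed-dose sentence. The rule is addressed to staff, who teach each family about the product dispensed, and anyone explaining granules would have to translate it. The diary and site materials, which are not among the documents, may already be correct. Early vomiting would be an occasional event within a 12- or 24-week course.

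Much of this stands as a limit on consequence. The intent probably is recoverable, and neither the frequency of the event nor the wording given to families is known. It does not rescue the sentence. 'An additional tablet' states a quantity in a way that 'the tablet' does not. For granules even a charitable reader must choose a replacement word, and 'packet' would be the wrong choice.

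A second objection is that a full same-day repeat sits awkwardly with two limits: the advice in 5.2.3 against a double dose, and the calendar-day maximum in 5.4 for GT-3 subjects. Both belong to text on missed or forgotten doses. Both apply equally to the existing extra-tablet rule, which for the 90/400 mg tablet is already a full repeat, so they are no reason to keep the present wording.

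**Conclusion.** The concern holds. As written, the vomiting rule is correct for 1 of 5 presentations and for none of the planned Group 2 doses. It replaces 50% or 25% of the multi-tablet doses and is undefined for granules. It is a wording error in a dosing instruction, and it should be corrected.

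The per-event figures take the sentence literally and compare it with repeating the full dose; the packet figures also rest on the substitution noted above. The roughly 120 of 220 describes who is on multi-unit regimens, not who would vomit early or be under-dosed. No effect on exposure, adherence or SVR12 is shown. Sample size, confidence-interval precision and the planned analyses are untouched. Confidence is high on the wording; the practical impact is unknown.

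**What to change.** In Protocol 5.2.3, change the vomiting rule so that the subject repeats the full assigned dose, meaning all tablets or all granule packets. For consistency only, change the reference to the tablet in the missed-dose sentence to the missed dose. The instruction for subjects on the single 90/400 mg tablet stays the same in effect.

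Use the same wording in the site administration instructions for both phases (6.3.1.1 and 6.4.1.1) and in the PK Lead-in dosing diary. The Treatment Phase schedule has no diary, so the site instructions must carry the wording there.

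The cost is two phrases in 5.2.3 and matching text in those materials, with no change to sample size, data collection or analysis.

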5.3. Ribavirin (GT-3 Subjects Only)

5.3.1. Description and Handling of RBV

5.3.1.1. Formulation

REBETOL capsules consist of a white powder in a white, opaque, gelatin capsule. Each capsule contains 200 mg ribavirin and the inactive ingredients microcrystalline cellulose, lactose monohydrate (40 mg), croscarmellose sodium, and magnesium stearate. The capsule shell contains gelatin, titanium dioxide. The capsule shell imprint contains shellac, propylene glycol, ammonium hydroxide, coloring agent (E 132). The hard capsule is imprinted with blue ink.

REBETOL RBV Oral Solution 40 mg per mL is a clear, colorless to pale or light yellow bubble gum-flavored liquid. In addition to the active ingredient, RBV oral solution contains the following inactive ingredients: sucrose, glycerin, sorbitol, propylene glycol, sodium citrate, citric acid, sodium benzoate, natural and artificial flavor for bubble gum #15864, and water.

5.3.1.2. Packaging and Labeling

The RBV capsules are packaged in blisters. Each blister card contains 20 capsules and seven cards (140 capsules) per carton.

The RBV oral solution is packaged in 4-oz amber glass bottles (100 mL/bottle) with child-resistant closures.

RBV capsules and oral solution to be distributed to centers in the US, EU and the rest of the countries shall be labeled to meet all applicable requirements of the US Food and Drug Administration (FDA) and Annex 13 of Good Manufacturing Practices: Manufacture of investigational medicinal products (February 2010) and/or other local regulations as applicable.

5.3.1.3. Storage and Handling

RBV capsules should not be stored above 30°C (86 °F).

RBV oral solution should not be stored above 30°C (86°F).

5.3.2. Dosage and Administration of RBV (GT-3 Subjects Only)

RBV dose will be administered by weight as follows:

Body Weight kg (lbs.)	RBV Daily Dose	RBV Number of Capsules
<47 (<103)	15 mg/kg/day	Use Oral Solution. Divided dose in the morning and evening.
47-49 (103-108)	600 mg/day	1 × 200-mg capsules A.M. 2 × 200-mg capsules P.M.
50-65 (110 – 143)	800 mg/day	2 × 200-mg capsules A.M. 2 × 200-mg capsules P.M.
66-80 (145 – 176)	1000 mg/day	2 × 200-mg capsules A.M. 3 × 200-mg capsules P.M.
81-105 (178-231)	1200 mg/day	3 × 200-mg capsules A.M. 3 × 200-mg capsules P.M.
>105 (>231)	1400 mg/day	3 × 200-mg capsules A.M. 4 × 200-mg capsules P.M.

* Note: Subjects with a body weight greater than or equal to 47 kg may utilize the RBV oral solution if necessary.

The morning dose of RBV will be taken with food and LDV/SOF FDC. The evening dose of RBV will be taken with food.

RBV will be supplied by Gilead Sciences for all subjects.

5.4. Co-administration of LDV/SOF FDC and RBV (GT-3 Subjects Only)

In the Treatment Phase of the study, each subject will be given instructions to maintain approximately the same daily dosing interval between study drug doses.

For **morning doses**, subjects will be instructed to take study drugs as follows:

- LDV/SOF FDC
- Weight-based RBV (as per Section 5.3.2).

For **evening doses**, subjects will be instructed to take study drug as follows:

- Weight-based RBV (as per Section 5.3.2).

If a subject forgets to take the study medication at the correct time, it may be taken later in the day; however, no more than the protocol specified dose of LDV/SOF FDC should be taken on any calendar day. The subject should resume the standing dosing schedule on the next day. Study medications should not be cut or split.

5.5. Study Drug Compliance

Subjects will be instructed to return any unused LDV/SOF FDC and/or RBV in the original container on Day 3 (PK Lead-in), Day 10 (PK Lead-in), and/or at study treatment visits every 4 weeks (Treatment Phase).

Returned medication will be reconciled by the investigator in order to monitor the subject's compliance with the medication regimen.

